***Grade 3 unsolicited AE(s) for the first 200 study participants through their Day 43 follow-up:***

- *Once the investigator or designee become aware that study participant(s) have experienced a Grade 3 unsolicited AE considered to be at least possibly related to vaccination, the investigator or designated study staff must complete information in the electronic Expedited AE Report in the eCRF **WITHIN 24 HOURS**. The report will always be completed as thoroughly as possible with all available details of the event.*
- *Even if the investigator does not have all information regarding a Grade 3 unsolicited AE considered to be at least possibly related to vaccination, the report should still be completed within 24 hours. Once additional relevant information is received, the report should be updated **WITHIN 24 HOURS**. The investigator will always provide an assessment of causality at the time of the initial report.*
- *The investigator will be required to confirm the review of the Grade 3 unsolicited AE(s) causality by ticking the “reviewed” box in the electronic Expedited AE Report within 72 hours of submission of the Grade 3 unsolicited AE(s).*
- *Refer to [Section 8.3.1](#) for the details on timeframes for reporting of AE(s).*

2.0	28OCT2021	PPD [REDACTED]	
Update following protocol amendment 1 dated 8th October 2021, CBER feedback and to complete the analysis specification:
 
 • Update reference to protocol amendment 1 • New study visit at Day 15 and safety call at Day 2-3 • SRT to be monthly rather than frequently • Update prior medication definition to include all medications started before first dose of study treatment • Ensure consistency on missing data • Varicella-like rash now includes injection site varicella-like rash • Clarified solicited and unsolicited adverse events analysis • Include intensity grades for fever and updated grades for varicella-like rash
3.0	25NOV2021	PPD [REDACTED]	
Update following protocol amendment 2 dated 15th November 2021:
 
 • Include general rash (not varicella-like), drowsiness, irritability and loss of appetite as solicited events

Document: \\quintiles.net\enterprise\Apps\sasdata\SASb\SAS\GlaxoSmithKline\VNS\217212\VNS 20-006\Biostatistics\Documentation\SAP\ GSK_217212\VNS 20-006_ZZA47662_SAP_Final_v7_24Jun2024.docx

Author: PPD Version Number: 7.0
 Version Date: 24Jun2024

Template No.: CS_TP_BS016 Revision 6

Reference: CS_WI_BS005

Effective Date: 02Dec2019

4.0	09JUN2022	PPD	Include countries other than the US. Prevnar 13 not administered in all countries. Include new analysis split by country, duration of solicited events and ongoing solicited events post the solicited period.
5.0	27SEP2022	PPD	Update following the Spanish protocol amendment – adding a co-administered meningococcal vaccine visit at Day 15 for Spain. Update algorithm in appendix 2 to be consistent with section 15.
6.0	04MAR2024	PPD	Reverted update made for the Spanish protocol amendment in SAP version 5. Added derivation for age. Added country as fixed effect to all models. Updated the MedDRA version number and Preferred Terms for Drowsiness and Loss of appetite. Updated Preferred Terms for unsolicited adverse events that are synonymous with solicited adverse events. Added details for handling duplicate solicited adverse events. Explained handling of solicited events recorded beyond the end of the solicited periods. Added definition of immediate unsolicited AEs.
7.0	24JUN2024	PPD	Added Section 18.1.1.1 eCOA Compliance.

1. LIST OF ABBREVIATIONS

AE	Adverse Event
ANOVA	Analysis of variance
ATC	Anatomical Therapeutic Chemical
CDISC	Clinical Data Interchange Standards Consortium
CI	Confidence Interval
COVID-19	Coronavirus disease 2019
CSR	Clinical Study Report
eCOA	Electronic Diary
eCRF	Electronic Case Report Form
ENR	Enrolled Set
ES	Exposed Set
gE	Glycoprotein E
GCP	Good Clinical Practice
GMC	Geometric Mean Concentration
IDMC	Independent Data Monitoring Committee
LAR	Legally Acceptable Representative
LL	Lower Limit
LLOQ	Lower Limit Of Quantification
MedDRA	Medical Dictionary for Regulatory Activities

Document: \\quintiles.net\enterprise\Apps\sasdata\SASb\SAS\GlaxoSmithKline\VNS\217212\VNS 20-006\Biostatistics\Documentation\SAP\ GSK_217212\VNS 20-006\ZZA47662_SAP_Final_v7_24Jun2024.docx

Author: PPD Version Number: 7.0
Version Date: 24Jun2024

Template No.: CS_TP_BS016 Revision 6

Reference: CS_WI_BS005

Effective Date: 02Dec2019

MMR	Measles, mumps, and rubella vaccine
PD	Protocol Deviation
PDMP	Protocol Deviations Management Plan
PPS	Per Protocol Set
PT	Preferred Term
SAE	Serious Adverse Event
SAP	Statistical Analysis Plan
SD	Standard Deviation
SOC	System Organ Class
SRT	Safety Review Team
TEAE	Treatment Emergent Adverse Event
VNS	Varicella vaccine (investigational vaccine)
VV	Varicella vaccine (comparator)

2. INTRODUCTION

This document describes the rules and conventions to be used in the presentation and analysis of immunogenicity and safety at final analyses for Protocol 217212 (VNS 20-006). It describes the data to be summarized and analyzed, including specifics of the statistical analyses to be performed.

This Statistical Analysis Plan (SAP) is based on protocol amendment 3 dated 18th May 2022.

Document: \\quintiles.net\enterprise\Apps\sasdata\SASb\SAS\GlaxoSmithKline\VNS\217212(VNS 20-006)\Biostatistics\Documentation\SAP\ GSK_217212(VNS 20-006)_ZZA47662_SAP_Final_v7_24Jun2024.docx

Author: PPD Version Number: 7.0
Version Date: 24Jun2024

Template No.: CS_TP_BS016 Revision 6

Reference: CS_WI_BS005

Effective Date: 02Dec2019

3. STUDY OBJECTIVES

3.1. PRIMARY OBJECTIVE

The primary objective is

- To evaluate the immune response of VNS vaccine (formulated with different potencies) and VV vaccine in terms of geometric mean concentration at Day 43

3.2. SECONDARY OBJECTIVES

The secondary objectives are

- To evaluate the immune response of VNS vaccine (formulated with different potencies) and VV vaccine in terms of seroresponse rate* at Day 43
- To evaluate safety and reactogenicity following administration of VNS and VV vaccines

3.3. ENDPOINTS

The primary endpoint is

- Anti-VZV gE antibody concentration at Day 43

The secondary endpoints are

- Seroresponse to gE at Day 43
- Solicited events
 - Percentage of participants reporting each solicited administration site event in terms of injection site redness, pain and swelling within 4 days (Day 1 to Day 4)

Document: \\quintiles.net\enterprise\Apps\sasdata\SASb\SAS\GlaxoSmithKline\VNS\217212\VNS 20-006\Biostatistics\Documentation\SAP\ GSK_217212\VNS 20-006_ZZA47662_SAP_Final_v7_24Jun2024.docx

Author: PPD Version Number: 7.0
Version Date: 24Jun2024

Template No.: CS_TP_BS016 Revision 6

Reference: CS_WI_BS005

Effective Date: 02Dec2019

- post-dose of VNS vaccine or VV vaccine
- Percentage of participants reporting each solicited systemic event in terms of fever, varicella-like rash+ and general rash (not varicella-like) within 43 days (Day 1 to Day 43) post-dose of study interventions at Day 1**
- Percentage of participants reporting each solicited systemic event in terms of drowsiness, loss of appetite and irritability within 15 days (Day 1 to Day 15) post-dose of study interventions at Day 1**
- Unsolicited Adverse Events (AEs)***
 - Percentage of participants reporting unsolicited AEs within 43 days (Day 1 to Day 43) post-dose of study interventions at Day 1**
- Serious Adverse Events (SAEs)
 - Percentage of participants reporting SAEs post-dose of study interventions at Day 1** up to the end of study

* Seroresponse rate is defined as the percentage of participants for whom post-dose of the study interventions (Day 43), the anti-VZV gE antibody concentration is ≥ 300 mIU/mL.

** Study interventions = VNS vaccine (investigational vaccine); VV vaccine (Varivax, comparator vaccine); MMR (*M-M-R II* or *M-M-RVaxPro*), *Havrix* and *Prevnar 13* (if applicable) vaccines (co-administered vaccines) at Day 1.

*** Unsolicited AEs include non-serious and serious AEs

+ Includes injection site varicella-like rash

4. STUDY DESIGN

4.1. GENERAL DESCRIPTION

This will be a phase II, observer-blind, randomized, multicenter controlled study with 5 parallel intervention groups of healthy children aged 12 to 15 months at the time of intervention. Participants will be randomized to receive a single dose of an investigational varicella vaccine (3 groups of 200 participants each receiving one of the 3 different vaccine potencies [a low, a medium, and a high potency of the VNS vaccine, respectively]) or a single dose of a comparator licensed varicella vaccine (2 groups of 100 participants each receiving one of the 2 different lots

Document: \\quintiles.net\enterprise\Apps\sasdata\SASb\SAS\GlaxoSmithKline\VNS\217212\VNS 20-006\Biostatistics\Documentation\SAP\ GSK_217212\VNS 20-006_ZZA47662_SAP_Final_v7_24Jun2024.docx

Author:	PPD	Version Number:	7.0
		Version Date:	24Jun2024

Template No.: CS_TP_BS016 Revision 6

Reference: CS_WI_BS005

Effective Date: 02Dec2019

of the VV vaccine, which will be pooled for all analyses).

The rationale of this study is to demonstrate the immunogenicity of the investigational VNS vaccine at 3 potencies compared with commercially available Merck's varicella vaccine, Varivax (hereafter designated as VV vaccine). In addition to assessing the immunogenicity of both varicella vaccines, this study intends to also generate safety data in the participants. All participants in the US will be co-administered with a measles, mumps and rubella vaccine (MMR vaccine), a hepatitis A vaccine (*Havrix*), and a 13-valent pneumococcal conjugate vaccine (*Prevnar 13*). Participants outside of the US will be co-administered with MMR, *Havrix* and in some countries, with *Prevnar 13*. Outside the US, *Prevnar 13* will only be administered in countries where pneumococcal conjugate is recommended at 12-15 months as per national immunization schedule. If *Prevnar 13* is to be administered, participants are required to have previously received the primary series of pneumococcal conjugate vaccine in their first year of life with last dose at least 60 days prior to study entry. There will be 3 in-person study visits, at Day 1 (intervention), when the participants receive study intervention, at Day 15 (either in-person or virtually, for review of post-vaccination safety data) and Day 43, as well as 1 safety call and 1 safety follow-up contact, at Day 2-3 and Day 181, respectively.

Healthy children aged 12 to 15 months will be enrolled in this study according to the inclusion and exclusion criteria (see protocol Section 5.0). Approximately 800 participants will be randomly assigned to the 5 study groups in a 2:2:2:1:1 ratio prior to intervention to provide approximately 200 enrolled participants per each VNS group and 100 enrolled participants per each VV group (VV Lot 1 and VV lot 2). Approximately 90% of the enrolled participants are expected to be included in the Per Protocol Set (PPS) and evaluated for immunogenicity.

Document: \\quintiles.net\enterprise\Apps\sasdata\SASb\SAS\GlaxoSmithKline\VNS\217212\VNS 20-006\Biostatistics\Documentation\SAP\ GSK_217212\VNS 20-006_ZZA47662_SAP_Final_v7_24Jun2024.docx

Author: PPD Version Number: 7.0
Version Date: 24Jun2024

Template No.: CS_TP_BS016 Revision 6

Reference: CS_WI_BS005

Effective Date: 02Dec2019

Study intervention Groups

Intervention groups	Number of participants	Age (Min-max)	Study interventions
VNS_Low	200	12-15 months	VNS_Low vaccine, MMR*, Havrix , Prevnar 13 **
VNS_Med	200	12-15 months	VNS_Med vaccine, MMR*, Havrix , Prevnar 13 **
VNS_High	200	12-15 months	VNS_High vaccine, MMR*, Havrix , Prevnar 13 **
VV_Lot 1	100	12-15 months	VV vaccine (Varivax Lot 1), MMR*, Havrix , Prevnar 13 **
VV_Lot 2	100	12-15 months	VV vaccine (Varivax Lot 2), MMR*, Havrix , Prevnar 13 **

* *M-M-R II* or *M-M-RVax Pro*, depending on the country. ** *Prevnar 13* will only be administered to participants enrolled in the US and in countries where pneumococcal conjugate vaccine is recommended at 12-15 months as per national immunization schedule.

Document: \\quintiles.net\enterprise\Apps\sasdata\SASb\SAS\GlaxoSmithKline\VNS\217212\VNS 20-006\Biostatistics\Documentation\SAP\ GSK_217212\VNS 20-006_ZZA47662_SAP_Final_v7_24Jun2024.docx

[figure not shown]
Author: PPD Version Number: 7.0
 Version Date: 24Jun2024

Template No.: CS_TP_BS016 Revision 6

Reference: CS_WI_BS005

Effective Date: 02Dec2019

Figure A: Study Schema

VNS_Low, VNS_Med, and VNS_High vaccine = VNS vaccine in low, medium, and high potency; VV_Lot 1 and VV_Lot 2 = VV vaccine in 2 lots

^a VV_Lot 1 and VV_Lot 2 groups will be analyzed as pooled groups

^b Contact (by telephone call or any other convenient procedure) for the safety follow-up will take place 6 months post-dose of study interventions

^c Study interventions: VNS vaccine (investigational vaccine) or VV vaccine (*Varivax*, comparator vaccine); MMR (*M-M-R II or M-M-RVaxPro*), *Havrix*, and *Prevnar 13* if applicable (co-administered vaccines) will be administered at Day 1. Note: *Prevnar 13* will only be administered to participants enrolled in the US and in countries where pneumococcal conjugate vaccine is recommended at 12-15 months as per national immunization schedule.

^d Recording in the electronic Case Report Form

Document: \\quintiles.net\enterprise\Apps\asadata\SASb\SAS\GlaxoSmithKline\VNS\217212\VNS 20-006\Biostatistics\Documentation\SAP\ GSK_217212\VNS 20-006_ZZA47662_SAP_Final_v7_24Jun2024.docx

Author: PPD Version Number: 7.0

Version Date: 24Jun2024

Template No.: CS_TP_BS016 Revision 6

Reference: CS_WI_BS005

Effective Date: 02Dec2019

^e Blood sampling for anti-varicella zoster virus enzyme-linked immunosorbent assay

^f Independent Data Monitoring Committee review details are provided in protocol Section 8.2.3

^g Visit 2 (Day 15) for review of post-vaccination safety data may be a virtual visit.

^h Safety call to remind completion of the electronic Diary/smartphone application and address any potential early post-vaccination safety concerns.

*Drowsiness, loss of appetite, irritability

**Fever, varicella-like rash (including injections site varicella-like rash) and general rash (not varicella like)

4.2. SCHEDULE OF EVENTS

Schedule of events can be found in Section 1.3 of the protocol.

4.3. CHANGES TO ANALYSIS FROM PROTOCOL

- No changes

5. PLANNED ANALYSES

The following analyses will be performed for this study:

- Analyses for Independent Data Monitoring Committee (IDMC) meetings
- Analyses for Safety Review Team (SRT) review
- Interim Analysis
- Final Analysis

5.1. INDEPENDENT DATA MONITORING COMMITTEE (IDMC)

An IDMC SAP, describing the methodology and the presentation of, and access to, results will be provided by IQVIA as a separate document.

Document: \\quintiles.net\enterprise\Apps\sasdata\SASb\SAS\GlaxoSmithKline\VNS\217212\VNS 20-006\Biostatistics\Documentation\SAP\ GSK_217212\VNS 20-006_ZZA47662_SAP_Final_v7_24Jun2024.docx

Author: PPD Version Number: 7.0
Version Date: 24Jun2024

Template No.: CS_TP_BS016 Revision 6

Reference: CS_WI_BS005

Effective Date: 02Dec2019

An IDMC will provide safety oversight during the active vaccination period, through unblinded review of the cumulative safety data.

An enrollment pause is foreseen for the first IDMC review after 200 participants (approximately 50 participants in each group, considering pooled VV groups) are enrolled and vaccinated. The analysis will take place once all 200 participants have returned for their Day 43 visit (Visit 3) or have withdrawn from the study, within the allowed interval for the visit. A positive outcome of the IDMC review will be a pre-requisite for the continuation of the study. A subsequent IDMC review meeting is planned during the study, after Day 43 safety follow-up of 400 participants is completed. No enrolment pause is foreseen after this.

5.2. SRT REVIEW

The SRT is responsible for ongoing safety monitoring. Monthly SRT reviews will occur up to the enrollment and vaccination of the first 200 participants through their Day 43 follow-up, to monitor cumulative, blinded safety data (including serious and non-serious AEs). The blinded safety data review by the SRT may trigger an emergency ad-hoc IDMC review before the 200 participants are enrolled and vaccinated.

5.3. INTERIM ANALYSIS

One interim analysis will take place for this study. A statistical analysis including safety and final immunogenicity data for all participants up to Day 43 timepoint is planned, the results of which will be based on the unblinded intervention groups. All analyses are descriptive and therefore no statistical adjustment for interim analyses is required.

5.4. FINAL ANALYSIS

All final, planned analyses identified in this SAP will be performed by IQVIA Biostatistics following Sponsor Authorization of this Statistical Analysis Plan, Database Lock, Sponsor Authorization of Analysis Sets and Unblinding of intervention group.

Document: \\quintiles.net\enterprise\Apps\sasdata\SASb\SAS\GlaxoSmithKline\VNS\217212\VNS 20-006\Biostatistics\Documentation\SAP\ GSK_217212\VNS 20-006_ZZA47662_SAP_Final_v7_24Jun2024.docx

Author: PPD Version Number: 7.0
Version Date: 24Jun2024

Template No.: CS_TP_BS016 Revision 6

Reference: CS_WI_BS005

Effective Date: 02Dec2019

This SAP is focused/limited to planned interim and final analyses. Outputs required for the final analyses will be flagged in the TFL mock shells document.

6. ANALYSIS SETS

Agreement and authorization of participants included/excluded from each analysis set will be conducted prior to the database lock.

6.1. PROCESS FOR ANALYSIS SET ASSIGNMENT

- Definitions for analysis sets are provided below.
- Prior to database lock, a transfer of raw data from the electronic Case Report Form (eCRF) will occur, and participants will be assigned to analysis sets in accordance with the definitions in this SAP and the available data at that time. However, the protocol deviations will be monitored continuously throughout the study.
- Listings presenting participants excluded from each preliminary analysis set and reasons for exclusion will be prepared for sponsor review ahead of database lock in order to allow appropriate related data queries to be issued.
- Listings presenting participants excluded from each final analysis set and reasons for exclusion will be prepared for sponsor review ahead of unblinding for a final review and approval. However, for deviations that can only be assessed after unblinding such as vaccination errors these will be reviewed after unblinding.
- A Data Review meeting will be held to confirm analysis set assignment for each participant and any changes will be recorded. Changes will be implemented, and an updated analysis set assignment will be approved by the sponsor.
- Sponsor authorization of the analysis sets will be necessary to unblind the data after database lock. Once approved, the study will be unblinded, analysis sets will be finalized including additional eliminations requiring unblinding, and the database will be locked.
- After database lock, the final analysis sets will be derived using the final study data, i.e., clinical database (eCRF), external vendor data (immunogenicity results), protocol deviations

Document: \\quintiles.net\enterprise\Apps\sasdata\SASb\SAS\GlaxoSmithKline\VNS\217212(VNS 20-006)\Biostatistics\Documentation\SAP\ GSK_217212(VNS 20-006)_ZZA47662_SAP_Final_v7_24Jun2024.docx

Author: PPD Version Number: 7.0
Version Date: 24Jun2024

Template No.: CS_TP_BS016 Revision 6

Reference: CS_WI_BS005

Effective Date: 02Dec2019

log and blinded data report.

6.2. ENROLLED SET [ENR]

All eligible participants who received a study intervention or were randomized. Note that as per Good Clinical Practice (GCP) enrolled participants' parent(s)/ legally acceptable representative (LAR) should have completed the informed consent process and participants should be eligible before initiating any study procedure.

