**Table 11 Analysis Sets**

Analysis set	Description
Enrolled Set	Participants who received a study intervention or were randomized. Note that as per GCP enrolled participants' parent(s)/LAR(s) should have completed the informed consent process and participants should be eligible before initiating any study procedure.
Exposed Set (ES)	All participants who received a study intervention. Analysis per group is based on the varicella intervention administered.
Per Protocol Set (PPS)	All eligible participants who received all study interventions as per protocol, were not unblinded, had immunogenicity results post-dose, complied with blood draw intervals (refer to Table 3 ), without intercurrent medical conditions that may interfere with immunogenicity and without prohibited concomitant medication/vaccination (see the footnote).

GCP = good clinical practice; LAR = legally acceptable representative

Note: Intercurrent medical conditions that may lead to elimination from the PPS are defined as confirmed immunodeficiency condition, or development of varicella or herpes zoster in the interval between study intervention administration and the collection of the blood specimen for immunogenicity at Visit 3.

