Child in care:	A child who has been placed under the control or protection of an agency, organization, institution or entity by the courts, the government or a government body, acting in accordance with powers conferred on them by law or regulation. The definition of a child in care can include a child cared for by foster parents or living in a care home or institution, provided that the arrangement falls within the definition above. The definition of a child in care does not include a child who is adopted or has an appointed legal guardian/LAR(s).
Combination product:	Combination product comprises any combination of 

• drug

• device

• biological product

	Each drug, device, and biological product included in a combination product is a constituent part.
Eligible:	Qualified for enrollment into the study based upon strict adherence to inclusion/exclusion criteria.
Enrollment:	The process of registering a participant into a clinical study by assigning participant identification number after signing the ICF.
Enrolled participant:	“Enrolled” means a participant’s parent’s/LAR’s agreement to participate in a clinical study following completion of the informed consent process. Potential participants who are screened for determining eligibility for the study, but do not participate in the study, are not considered enrolled.
Essential documents:	Documents which individually and collectively permit evaluation of the conduct of a study and the quality of the data produced.

Evaluable:	Meeting all eligibility criteria, complying with the procedures defined in the protocol, and, therefore, included in the per protocol analysis.
Immunological correlate of protection:	A correlate of risk that has been validated to predict a certain level of protection from the targeted endpoint.
Intervention:	Term used throughout the clinical study to denote a set of investigational product(s) or marketed product(s) or placebo intended to be administered to a participant.
Invasive medical device:	A device which, in whole or in part, penetrates inside the body, either through a body orifice or through the surface of the body

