6.3. EXPOSED SET [ES]

All participants who received a study intervention. Analysis per group is based on the varicella intervention administered.

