7. GENERAL CONSIDERATIONS

Data will be summarized descriptively (frequency and percentage for categorical data and mean, standard deviation [SD] and range for continuous data, unless specified otherwise). In summary

Document: \\quintiles.net\enterprise\Apps\lasdata\SASb\SAS\GlaxoSmithKline\VNS\217212(VNS 20-006)\Biostatistics\Documentation\SAP\ GSK_217212(VNS 20-006)_ZZA47662_SAP_Final_v7_24Jun2024.docx

Author: PPD Version Number: 7.0
Version Date: 24Jun2024

Template No.: CS_TP_BS016 Revision 6

Reference: CS_WI_BS005

Effective Date: 02Dec2019

tables for categorical data for which categories are defined on the eCRF, all categories will be presented as specified, even if the participant count within that category is zero.

In all the summary tables intervention VV lot 1 and VV lot 2 will be analyzed as pooled lots.

Unless otherwise specified, all data collected during the trial will be presented in listings for the ENR.

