10. DISPOSITION AND WITHDRAWALS

All participants who are enrolled in the study (those who received a study intervention at Day 1 or were randomized) will be accounted for in this study.

Document: \\quintiles.net\enterprise\Apps\sasdata\SASb\SAS\GlaxoSmithKline\VNS\217212\VNS 20-006\Biostatistics\Documentation\SAP\ GSK_217212\VNS 20-006_ZZA47662_SAP_Final_v7_24Jun2024.docx

Author: PPD Version Number: 7.0
Version Date: 24Jun2024

Template No.: CS_TP_BS016 Revision 6

Reference: CS_WI_BS005

Effective Date: 02Dec2019

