10.1. DISPOSITION

Participant disposition, withdrawals, and reasons for exclusion from each analysis set, including inclusion as well as exclusion criteria will be presented for the ENR. Specifically, the number of participants, vaccinated, completed the study, discontinuing the study and the reason for discontinuation will be summarized by study group for the ENR. Additionally, the number of participants returning for each visit for the ES will be presented.

A listing of the disposition for all participants with early withdrawal or discontinuation due to having Coronavirus Disease 2019 (COVID-19) or COVID-19 related issues information will be provided.

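### SAP 6.2 limits the Enrolled Set to eligible children, against Protocol Table 11 and SAP Section 10, so the disposition table cannot show the eligibility failures it is meant to report

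*SAP*

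**What the plan says.** Three places describe who counts as enrolled, and they do not agree.

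- **Protocol Table 11:** "Participants who received a study intervention or were randomized". Eligibility appears only in an accompanying note on Good Clinical Practice, as an expectation and not as a membership condition.
- **SAP 6.2:** "All eligible participants who received a study intervention or were randomized". The same note follows, but eligibility is now part of the definition itself.
- **SAP Section 10, opening:** "All participants who are enrolled in the study (those who received a study intervention at Day 1 or were randomized) will be accounted for". There is no eligibility condition.

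Eligible is a defined term in the protocol glossary: "Qualified for enrollment into the study based upon strict adherence to inclusion/exclusion criteria". SAP 4.3 lists no changes to the analysis from the protocol.

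The other relevant rules are these:

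- **ES (SAP 6.3):** "All participants who received a study intervention", with no eligibility condition.
- **Disposition (SAP 10.1):** "reasons for exclusion from each analysis set, including inclusion as well as exclusion criteria will be presented for the ENR". The number vaccinated is also summarised on the ENR.
- **Listings (SAP Section 7):** unless another population is specified, "all data collected during the trial will be presented in listings for the ENR".
- **Medical and vaccination history (SAP Section 13) and COVID-19 data (SAP Section 12):** presented or listed for the ENR.

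**The concern.** A participant-flow table should start from everyone randomised or dosed and show where each child left. A condition that removes ineligible children from the starting set defeats that purpose, because a child found ineligible after randomisation is one of the cases the table exists to report.

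Two things are at stake. First, the ES would no longer be contained in the ENR, so the number vaccinated in the disposition table could be smaller than the denominator of the safety tables, with nothing in the table to explain the gap. Second, the medical history of a child enrolled against the criteria, which a reader would want to see, would be left out of the output meant to hold it. Protocol Section 2.2 says the investigational vaccine has not been given to humans before, so a full account of who was randomised and dosed is a basic reporting need.

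**Working it through.** The plan gives no figure for this point, so the check is one of set membership, followed by an illustration of size.

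**Step 1. Apply each definition to each kind of child.**

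| Child | Protocol Table 11 ENR | SAP 6.2 ENR | SAP 10 enrolled | ES |
|---|---|---|---|---|
| Eligible, randomised, vaccinated | in | in | in | in |
| Eligible, randomised, not vaccinated | in | in | in | out |
| Eligible, vaccinated, not randomised | in | in | in | in |
| Ineligible, randomised, vaccinated | in | **out** | in | in |
| Ineligible, randomised, not vaccinated | in | **out** | in | out |
| Ineligible, vaccinated, not randomised | in | **out** | in | in |

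The protocol and SAP Section 10 columns agree in every row. SAP 6.2 differs from both in all three ineligible rows and in no others. In two of those rows the child is in the ES but not in the ENR. In the other the child is in neither set, and cannot be in the Per Protocol Set (PPS), which requires both eligibility and receipt of all study interventions.

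**Step 2. Which wording would be programmed?** SAP 6.1 assigns participants to sets by the definitions in the SAP, and 6.2 is the section that defines the ENR. Taken literally, the narrower wording applies.

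**Step 3. Consequence for SAP 10.1.** Failing the criteria means not eligible, and not eligible means not in the 6.2 ENR. The number of eligibility failures an ENR table can show is therefore 0, whatever the true number.

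**Step 4. Size.** The target is 800 participants (Protocol 9.2). Neither document gives an ineligibility rate, so k is an assumption. Suppose k ineligible children are among 800 who were all randomised and vaccinated:

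- ENR under SAP 6.2 = 800 − k
- ENR under Protocol Table 11 = 800
- ES = 800
- Ratio of ES to ENR under 6.2 = 800 / (800 − k)

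| k | k/800 | ENR under 6.2 | ES / ENR | Failures shown under 6.2 | Failures shown under Table 11 |
|---|---|---|---|---|---|
| 1 | 0.125% | 799 | 100.1% | 0 | 1 |
| 8 | 1% | 792 | 101.0% | 0 | 8 |
| 16 | 2% | 784 | 102.0% | 0 | 16 |
| 24 | 3% | 776 | 103.1% | 0 | 24 |
| 40 | 5% | 760 | 105.3% | 0 | 40 |

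The count of PPS exclusions shown for the ENR shifts as well. With the protocol's planning value of 10% unevaluable, 80 of 800 are excluded (10.0%). If 8 of those 80 are ineligible, the 6.2 table shows 80 − 8 = 72 of 792 (9.09%).

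**The case against.** The strongest reply is that the section governing disposition carries the right wording. SAP Section 10 describes the enrolled as "those who received a study intervention at Day 1 or were randomized", and the request in 10.1 for criteria failures makes sense only if ineligible children are in the table. A programmer might follow that intent. This stands in part: the SAP contradicts itself, and the omission depends on which wording is followed. It does not remove the problem, because 6.2 is the definition and 6.1 directs assignment by definition.

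A second reply is that such children are seen elsewhere. This also stands in part. SAP 10.2 tabulates important deviations, meaning those linked to elimination from the PPS, on the ES. SAP 10.1 gives visit-return counts on the ES. SAP 6.1 provides listings of participants excluded from each set, with reasons, for sponsor review. None of these repairs the disposition table, and the ES-based tables do not reach a child who was never vaccinated.

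A reader might infer three stronger things that the documents do not support:

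- **That safety tables would hold children missing from the safety listings.** The ENR default for listings applies only where nothing else is specified, and SAP Section 18 bases all safety outputs on the ES.
- **That eligibility failures would be reported nowhere.** A vaccinated ineligible child is eliminated from the PPS, and so should be counted in the ES-based important-deviation table.
- **That every ineligible randomised child is in the ES.** Only vaccinated children are.

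The number affected may also be small. Protocol Section 5.0 allows no waivers of enrolment criteria, and Section 6.3.3 requires eligibility to be checked before allocation.

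**Conclusion.** The point holds as an error in the written definition. SAP 6.2 contradicts Protocol Table 11 and SAP Section 10, and SAP 4.3 does not declare the difference. Applied as written, it gives a wrong participant flow as soon as one randomised or dosed child is found ineligible: the ENR falls short by each such child, and the eligibility failures shown in the ENR disposition table are 0.

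The effect is confined to the disposition table and to non-safety outputs based on the ENR. Safety outputs and the important-deviation table use the ES, and immunogenicity on the PPS already carries its own eligibility condition, so none of these results changes. The conclusion rests on reading 6.2 literally and eligible in its glossary sense. The values of k above are illustrations only, since the documents give no rate.

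**What to change.** Delete the word eligible from the SAP 6.2 definition and keep the Good Clinical Practice note as it stands. The ENR then matches Protocol Table 11 and the opening of SAP Section 10, the ES is again contained in the ENR, and the table in SAP 10.1 can report what it is asked to report. The statement in SAP 4.3 that nothing has changed becomes correct on this point.

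The cost is one word in the SAP and a check that the programmed ENR flag follows it. No protocol change is needed, and nothing useful is lost, because the PPS definition in SAP 6.4 has its own eligibility requirement.
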